
 To further evaluate the safety of belantamab mafodotin administered in combination with pembrolizumab in subjects with RRMM To further assess the clinical activity of the combination treatment with belantamab mafodotin and pembrolizumab in subjects with RRMM 	
 Number (percent) of subjects with AEs, changes in clinical signs and laboratory parameters Ocular finding on ophthalmic exam Clinical benefit rate (CBR), defined as the percentage of participants with a confirmed minimal response (MR) or better per IMWG Duration of response (DoR), defined as: the time from first documented evidence of PR or better, to the time when disease progression (PD) is documented per IMWG; or death due to PD occurs among subjects who achieve an overall response, i.e. confirmed PR or better Time to response (TTR), defined as: the time between the date of first dose and the first documented evidence of response (PR or better) among participants who achieved a confirmed response of PR or better Time to best response, defined as the time between the date of first dose and the first best documented response (PR or better) among subjects who achieved a confirmed response of PR or better Progression-free survival (PFS), defined as: the time from first dose until the earliest date of PD per IMWG, or death due to any cause Time to disease progression (TTP), defined as: the time from first dose until the earliest date of PD per IMWG, or death due to PD Overall Survival (OS), defined as the time from first dose until death due to any cause

 To evaluate the pharmacokinetic 	
 Pharmacokinetic (PK) parameters following IV

Objectives	Endpoints
profile of belantamab mafodotin when administered intravenously in combination with pembrolizumab ¹	administration as data permit.
• To assess ADAs against belantamab mafodotin ¹	• Incidence and titer of ADA to belantamab mafodotin
Exploratory Objectives	Exploratory Endpoints
• To assess Minimal Residual Disease (MRD) in participants who achieve \geq VGPR or better	• Minimal Residual Disease (MRD) negativity rate, defined as: the percentage of subjects who are MRD negative in subjects who achieve VGPR or CR

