7.2.2. Secondary Efficacy Analyses

7.2.2.1. Endpoint / Variables

CBR

Clinical Benefit Rate (CBR), defined as the percentage of participants with a confirmed MR or better (i.e., MR, PR, VGPR, CR and sCR) as the BOR assessed by the investigator per IMWG (2016).

DOR

Duration of response (DoR), defined as the interval of time (in months) from first documented evidence of confirmed PR or better to the time when disease progression is documented assessed by the investigator per IMWG (2016), or death due to PD among participants with a confirmed PR or better as the BOR. Responders without confirmed PD will be censored at the censoring time point for time to progression as specified in [Table 6](#).

TTR

Time to response (TTR), defined as the interval of time (in months) between the date of first dose and the first documented evidence of response (PR or better) among participants with a confirmed PR or better as the BOR assessed by the investigator per IMWG (2016).

TTBR

Time to best response (TTBR), defined as the interval of time (in months) between the date of first dose and the earliest date of achieving BOR among participants with a confirmed PR or better as the BOR assessed by investigator per IMWG (2016).

PFS

Progression-free survival (PFS), defined as the interval of time (in months) from first dose until the earlier date of disease progression per IMWG (2016), or the date of death due to any cause. Determination of dates of PFS events and dates for censoring are described in [Table 5](#).

TTP

Time to disease progression (TTP), defined as the interval of time (in months) from first dose until the earlier date of PD per IMWG (2016), or the date of death due to PD. Determination of dates of TTP events and dates for censoring are described in [Table 6](#).

OS

Overall Survival (OS), defined as the interval of time (in months) from first dose to the date of death due to any cause. Participants who withdraw consent from the study or are lost to follow-up will be censored at the time of withdrawal or lost to follow-up. Participants who do not have a death record at the clinical cut-off date for the analysis will be censored at the last known alive date. The last contact date will be determined by

the maximum collection/assessment date from among selected data domains within the clinical database.

Table 5 Assignments of Progression and Censoring Dates for PFS Analysis

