Situation	Date of Event (Progression/Death due to PD) or Censored ¹	Event (Progression/Death due to PD) Or Censored
No adequate baseline assessments ⁴ and the subject has not died (if the subject has died due to PD follow the rules for death indicated at the bottom of the Table)	First dose	Censored
No post-baseline assessments and the subject has not died (if the subject has died due to PD follow the rules for death due to PD indicated at the bottom of the Table)	First dose	Censored
Progression documented between scheduled visits	Date of assessment of progression	Event
With post-baseline assessment but no progression (or death due to PD)	Date of last 'adequate' assessment of response ²	Censored
No adequate post-baseline assessment before start of new anticancer therapy	First dose	Censored
With adequate post-baseline assessment and new anticancer treatment started (prior to documented disease progression). ³	Date of last 'adequate' assessment of response ² (on or prior to starting anti-cancer therapy)	Censored
Death due to PD before first scheduled assessment (or Death at baseline or without any adequate assessments)	Date of death	Event
Death due to PD between adequate assessment visits	Date of death	Event
Death from causes other than PD before first scheduled assessment (or Death at baseline or without any adequate assessments)	Date of death	Censored
Death from causes other than PD between adequate assessment visits	Date of death	Censored
Death due to PD or progression after more than three missed scheduled assessment	Date of last 'adequate' assessment of response ² (prior to missed assessments): If the disease assessment is every 3 weeks, a window of 66 days (9 weeks + 3 day window) will be used to determine whether there is extended time without adequate assessment. If the time difference between PD/death due to PD and last adequate disease assessment is	Censored

CONFIDENTIAL

205207

Situation	Date of Event (Progression/Death due to PD) or Censored ¹	Event (Progression/Death due to PD) Or Censored
	more than 66 days, PFS will be censored at the last adequate disease assessment prior to PD/death due to PD.	

¹ Event or censored are based on confirmed responses.

² An adequate assessment is defined as an assessment where the investigator assessed response is sCR, CR, PR, VGPR, MR, or SD .

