7.2.2.2. Summary Measure

CBR

The number and percentage of participants with the BOR in the following response categories will be summarized by dose level: sCR, CR, VGPR, PR, MR, clinical benefit response (sCR+CR+VGPR+PR+MR), SD, PD, and NE. The corresponding exact 95% CI for CBR will also be provided. Participants with unknown or missing responses will be treated as non-responders, i.e., these participants will be included in the denominator when calculating percentages of response.

DOR

If there are sufficient number of responders who subsequently progress or die due to PD, distribution of DOR will be summarized using the Kaplan-Meier method. The median, 25th and 75th percentiles of DOR will be estimated and corresponding 95% confidence intervals will be estimated using the [Brookmeyer](#)-Crowley method (1982). A Figure and listing of DoR time will also be provided.

TTR

If there are sufficient number of responses by dose level, time to response at will be summarized descriptively using median(s) and quartiles in the subset of subjects with a confirmed response of PR or better as the BOR and corresponding 95% confidence intervals will be estimated using the [Brookmeyer](#)-Crowley method (1982). A Figure and listing of TTR time will also be provided.

TTBR

If there are sufficient number of responses by dose level, time to best response at will be summarized descriptively using median(s) and quartiles in the subset of subjects with a confirmed response of PR or better as the BOR and corresponding 95% confidence intervals will be estimated using the [Brookmeyer](#)-Crowley method (1982). A Figure and listing of TTBR time will also be provided.

PFS

The distribution of PFS for each dose level will be estimated using the Kaplan-Meier method. If there is a sufficient number of progressions or death due to PD, the median, 25th and 75th percentiles of PFS will be estimated and corresponding 95% confidence intervals will be estimated using the [Brookmeyer](#)-Crowley method (1982). PFS rate at 6, 9, 12, 15, and 18 months and corresponding 95% CI will also be estimated from the Kaplan-Meier analysis. A Figure and listing of PFS time will also be provided.

OS

The distribution of OS for each dose level will be estimated using the Kaplan-Meier method. If there are a sufficient number of deaths, then the median, 25th and 75th percentiles of OS will be estimated and corresponding 95% confidence intervals will be

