estimated using the [Brookmeyer-Crowley](#) method (1982). A graph of survival curves and a listing of survival times will also be provided. In addition, pending on maturity of data, the survival probability at 6, 9, 12, 15, and 18 months with 95% CI will be estimated using Kaplan-Meier method.

TTP

The distribution of TTP will be estimated using the Kaplan-Meier method. The median, 25th and 75th percentiles of TTP will be estimated and corresponding 95% confidence intervals will be estimated using the [Brookmeyer-Crowley](#) method (1982). A Figure and listing of TTP time will also be provided.

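### DoR and TTP censor deaths not due to PD, so the headline DoR runs longer than time to PD or any death; Table 6 also gives such deaths two possible censoring dates

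*SAP*

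**What the plan says.** The SAP defines TTP as time from first dose "until the earlier date of PD per IMWG (2016), or the date of death due to PD". DoR runs from first evidence of confirmed response to documented progression, "or death due to PD among participants with a confirmed PR or better as the BOR". The objectives table in Section 2.2 has the same restriction ("death due to PD occurs among subjects who achieve an overall response").

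For DoR censoring, Section 7.2.2.1 states: "Responders without confirmed PD will be censored at the censoring time point for time to progression as specified in" Table 6. That table has two rows for other deaths, "Death from causes other than PD before first scheduled assessment" and "Death from causes other than PD between adequate assessment visits". Both give the date of death, censored.

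Section 7.2.2.2 fixes the estimator: "The distribution of TTP will be estimated using the Kaplan-Meier method" and, given enough events, "distribution of DOR will be summarized using the Kaplan-Meier method". Medians and quartiles are planned for both. Landmark rates are planned only for PFS and OS.

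PFS (Table 5) counts death from any cause as an event, unless it falls more than 66 days after the last adequate assessment. In the list of displays, DoR (Table 2.004) and PFS (Table 2.007) are headline outputs; TTP (Table 2.008) is not.

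**The concern.** Kaplan-Meier treats a censored subject as someone who could still have the event. A subject who has died of another cause cannot progress. This has two consequences, which refer to different targets:

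- **DoR.** Read as the time a responder stays alive and progression-free, the planned estimate is too long. A responder who dies of toxicity is censored in DoR, while the same death within the assessment window is a PFS event.
- **TTP.** One minus Kaplan-Meier exceeds the cumulative incidence of PD, the proportion of subjects who actually progress.

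The DoR consequence matters more. DoR is headline output in a single-arm trial, and no planned display gives it with every death as an event. For TTP, PFS partly fills that role.

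There is also a drafting question. If Table 6 does not fix one censoring date for a non-PD death, two programmers can build different TTP and DoR datasets from the same records.

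**Working it through.** **Size of the shift.** The SAP states no figure for TTP, DoR or non-PD deaths, so there is none to reproduce. Two inputs come from the SAP: 28 subjects (Section 3.1.2.1) and the alternative ORR of 60% (Section 2.4.2), giving 0.60 × 28 = 16.8, about 17 responders. The rest is assumed: constant hazards, a PD-only median of 12 months for DoR and 6 months for TTP, and a non-PD death hazard equal to r times the PD hazard, with r = 0.10, 0.20, 0.30.

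*DoR.* With PD hazard h = ln 2 / 12, the hazard of PD or any death is h(1 + r), so the any-cause median is 12/(1 + r). For scale, the standard error of an uncensored exponential median is about m/(ln 2 × √n) = 12/(0.693 × 4.12) = 4.2 months. Censoring would make it larger.

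| r | PD-only median | Any-cause median | Difference | In SE |
|---|---|---|---|---|
| 0.10 | 12.0 | 10.9 | 1.1 | 0.3 |
| 0.20 | 12.0 | 10.0 | 2.0 | 0.5 |
| 0.30 | 12.0 | 9.2 | 2.8 | 0.7 |

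The ratio of the two medians is 1 + r whatever the PD-only median.

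*TTP.* With h = ln 2 / 6, 1 − KM at t is 1 − exp(−ht). The cumulative incidence is [1/(1 + r)] × [1 − exp(−h(1 + r)t)].

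- At 12 months, 1 − KM = 1 − 0.25 = 75.0%. The cumulative incidence at r = 0.20 is (1 − 0.25^1.2)/1.2 = 0.8105/1.2 = 67.5%. At r = 0.10 and 0.30 it is 71.1% and 64.2%. These rates only illustrate the curve; the SAP does not plan them.
- For the planned median, the cumulative incidence reaches 50% at −ln(1 − (1 + r)/2)/[h(1 + r)] = 6.3, 6.6 and 7.0 months, against 6.0 by Kaplan-Meier. With 28 subjects the SE is about 6/(0.693 × 5.29) = 1.6 months, so the shifts are about 0.2, 0.4 and 0.6 SE.

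The directions differ in meaning. Counting every death shortens DoR, which is less favourable to the regimen. Replacing 1 − KM by the cumulative incidence lowers the progression figure, which is more favourable.

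**Table 6 against Table 5.**

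1. Table 5's row for subjects assessed after baseline without progression excludes anyone who died. Table 6 narrows the exclusion to death due to PD. A non-PD death after a post-baseline assessment therefore fits that row (censored at the last adequate assessment) and also the non-PD death row (censored at death). Table 4 ends with a rule to take the first criterion that applies; Tables 5 and 6 have none. Borrowing it here would override the between-visits non-PD death row.
2. Table 5's 66-day gap rule covers any death. Table 6's covers only PD and death due to PD.
3. Table 6's gap text says that PFS will be censored, although the table is for TTP.

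Illustration: last adequate assessment on day 100, non-PD death on day 220, a gap of 120 days. Table 5 censors PFS at day 100. Under Table 6, TTP is censored at day 220 by the death row or at day 100 by the general row. The first reading adds 120 days without an assessment.

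**The case against.** The strongest defence is that the PD-only event is a deliberate choice, stated the same way in Sections 2.2 and 7.2.2.1, and Section 2.1 reports no change from the protocol's planned analysis. That stands: this is not a contradiction between definitions, and Kaplan-Meier with other deaths censored is a recognised estimator of a particular target. Deaths are not hidden either. PFS is also headline output, and OS, the summary of deaths (Table 3.0058), fatal adverse events (Table 3.0047) and a by-subject DoR listing (Listing 1.0014) are planned. All these endpoints are secondary and descriptive. The size rests wholly on assumed death rates and stays under one SE. None of this, however, supplies a DoR estimate with death from any cause as an event.

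Two stronger readings are tempting:

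- A reader might infer that subjects who died are counted as still responding. The SAP does not do that. They leave the risk set at death and no response time is credited afterwards.
- A reader might infer that toxic deaths flatter the regimen on both endpoints. That fits DoR only. For TTP, the cumulative incidence falls as non-PD deaths rise, so moving to it would make the regimen look better.

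On Table 6, the defence can say that crediting unobserved time is only one of two readings. True, and that is the defect: the table does not choose between them.

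**Conclusion.** The point holds in a limited form. As planned, DoR is longer than time to PD or any death, and 1 − KM for TTP exceeds the cumulative incidence of PD. These are two targets with opposite implications for the regimen, and neither shows that the chosen definition is wrong. Under constant hazards and a 12-month PD-only median, the any-cause DoR median is about 1.1 to 2.8 months shorter over the assumed range, or 0.3 to 0.7 SE with 17 responders. With few non-PD deaths the difference is negligible. The documents do not say how many to expect, nor which event definition any external comparator uses, so they do not support a claim of material bias.

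The Table 6 defect needs no assumption about rates. Overlapping rows without a tie-break, a gap rule that omits non-PD deaths, and a misnamed endpoint leave the censoring date open for both TTP and DoR.

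**What to change.** Keep the protocol definitions of TTP and DoR, and:

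1. Add to Table 2.004 and Figure 2.003 a supplementary DoR with death from any cause as an event, using the Table 5 rules for events and censoring.
2. In Table 6, make one row govern non-PD deaths, exclude them from the general no-progression row, and censor at the last adequate assessment when the gap to death exceeds 66 days. Correct the reference to PFS in the gap text.
3. Optionally, show the cumulative incidence of PD or death due to PD, with other deaths as a competing event, beside the TTP Kaplan-Meier estimate. Label it as a different target, not as a correction for toxic deaths.

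The cost is a wording change and one or two extra programmed estimates from data already collected. The supplementary DoR will be slightly less favourable than the planned one if any responder dies of another cause before progressing.

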7.2.2.2. Summary Measure

CBR

The number and percentage of participants with the BOR in the following response categories will be summarized by dose level: sCR, CR, VGPR, PR, MR, clinical benefit response (sCR+CR+VGPR+PR+MR), SD, PD, and NE. The corresponding exact 95% CI for CBR will also be provided. Participants with unknown or missing responses will be treated as non-responders, i.e., these participants will be included in the denominator when calculating percentages of response.

DOR

If there are sufficient number of responders who subsequently progress or die due to PD, distribution of DOR will be summarized using the Kaplan-Meier method. The median, 25th and 75th percentiles of DOR will be estimated and corresponding 95% confidence intervals will be estimated using the [Brookmeyer](#)-Crowley method (1982). A Figure and listing of DoR time will also be provided.

TTR

If there are sufficient number of responses by dose level, time to response at will be summarized descriptively using median(s) and quartiles in the subset of subjects with a confirmed response of PR or better as the BOR and corresponding 95% confidence intervals will be estimated using the [Brookmeyer](#)-Crowley method (1982). A Figure and listing of TTR time will also be provided.

TTBR

If there are sufficient number of responses by dose level, time to best response at will be summarized descriptively using median(s) and quartiles in the subset of subjects with a confirmed response of PR or better as the BOR and corresponding 95% confidence intervals will be estimated using the [Brookmeyer](#)-Crowley method (1982). A Figure and listing of TTBR time will also be provided.

PFS

The distribution of PFS for each dose level will be estimated using the Kaplan-Meier method. If there is a sufficient number of progressions or death due to PD, the median, 25th and 75th percentiles of PFS will be estimated and corresponding 95% confidence intervals will be estimated using the [Brookmeyer](#)-Crowley method (1982). PFS rate at 6, 9, 12, 15, and 18 months and corresponding 95% CI will also be estimated from the Kaplan-Meier analysis. A Figure and listing of PFS time will also be provided.

OS

The distribution of OS for each dose level will be estimated using the Kaplan-Meier method. If there are a sufficient number of deaths, then the median, 25th and 75th percentiles of OS will be estimated and corresponding 95% confidence intervals will be

estimated using the [Brookmeyer-Crowley](#) method (1982). A graph of survival curves and a listing of survival times will also be provided. In addition, pending on maturity of data, the survival probability at 6, 9, 12, 15, and 18 months with 95% CI will be estimated using Kaplan-Meier method.

TTP

The distribution of TTP will be estimated using the Kaplan-Meier method. The median, 25th and 75th percentiles of TTP will be estimated and corresponding 95% confidence intervals will be estimated using the [Brookmeyer-Crowley](#) method (1982). A Figure and listing of TTP time will also be provided.

7.2.2.3. Population of Interest

The secondary efficacy analyses will be based on the All Treated population, unless otherwise specified.

7.2.2.4. Statistical Analyses / Methods

Details of the planned displays are provided in [Appendix 11: List of Data Displays](#) and will be based on GSK data standards and statistical principles.

Unless otherwise specified, endpoints / variables defined in Section [7.2.2.1](#) will be summarised using descriptive statistics, graphically presented (where appropriate) and listed.

7.2.3. Exploratory Efficacy Analyses

7.2.3.1. Endpoint / Variables

MRD Negativity Rate

MRD negativity rate is defined in Section [7.1.2.1](#).

7.2.3.2. Summary Measure

MRD Negativity Rate

The summary measure of MRD negativity rate is provided at Section [7.1.2.2](#).

7.2.3.3. Population of Interest

The MRD negative rate analyses will be based on the All Treated population, unless otherwise specified.

7.2.3.4. Statistical Analyses / Methods

Details of the planned displays are provided in [Appendix 11: List of Data Display](#), based on GSK data standards.

Unless otherwise specified, endpoints / variables defined in Section 7.1.2.1 will be summarised using descriptive statistics, graphically presented (where appropriate) and listed.

7.3. Other Efficacy Analyses

7.3.1. Endpoint / Variables

Time to Next Treatment

Time to next treatment (TTNT) is defined as the time from the date of first dose of study treatment to the date of next subsequent treatment for relapse refractory multiple myeloma due to any reasons. Subjects who have not started the next subsequent anti-cancer treatment will be censored at the date of last contact or at death. Subjects who do not have a documented start date of first dose of study treatment will be excluded from this analysis.

Rate of VGPR or Better

Rate of VGPR or better, defined as the percentage of participants with a confirmed VGPR or better as the BOR (i.e., VGPR, CR and sCR), per IMWG (2016).

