7.3.2. Summary Measure

Time to Next Treatment

If there are sufficient number of responders who started new anti-cancer treatment due to any reasons by dose level, time to next treatment will be summarized descriptively using median(s) and quartiles.

Rate of VGPR or Better

The number and percentage of participants with the BOR in the following response categories will be summarized: sCR, CR, and VGPR. The corresponding exact 95% CI for rate of VGPR or better will also be provided. Participants with unknown or missing responses will be treated as non-responders, i.e., these participants will be included in the denominator when calculating percentages of response.

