7.3.3. Population of Interest

Time to next treatment and rate of VGPR or better analyses will be based on the All Treated population, unless otherwise specified.

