2.0010	All Treated	TTE1	Summary of Time to Next Treatment (GSK2857916 2.5 mg/kg)	Report for: 2.5 mg/kg doses only; Refer to Section 5.1 and use only code A, code D, and code H for dose level	P-SAC [3], F-SAC [4]

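### Time to next treatment is censored at death, a competing event, with no estimator named; separately, its summary depends on responders although the endpoint covers all treated subjects

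*SAP*

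**What the plan says.** SAP section 7.3.1 gives this definition of TTNT: "the time from the date of first dose of study treatment to the date of next subsequent treatment for relapse refractory multiple myeloma due to" (the sentence goes on to allow every reason). Death is not part of the event. For subjects without the event the rule is: "Subjects who have not started the next subsequent anti-cancer treatment will be censored at the date of last contact or at death".

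Section 7.3.2 sets a condition for the summary, "If there are sufficient number of responders who started new anti-cancer treatment due to any reasons by dose level", and then says that "time to next treatment will be summarized descriptively using median(s) and quartiles". Section 7.3 has no methods subsection. No estimator, confidence interval or competing-risk method is named for TTNT, and no sensitivity analysis is planned.

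Section 7.3.3 fixes the population: "Time to next treatment and rate of VGPR or better analyses will be based on the All Treated population, unless otherwise specified". Table 2.0010 in section 16.11.5 repeats All Treated. It stands under the time-to-event endpoints, uses shell TTE1 for the 2.5 mg/kg groups, and is planned for both the primary and the final analysis.

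**The concern.** A subject who has died can no longer start another therapy. Censoring at death treats that subject like one whose follow-up merely stopped. Under Kaplan-Meier, the death is in effect replaced by the later experience of those still alive and untreated. The resulting median is not the time by which half of the treated subjects have started next therapy, nor the time by which half have either started it or died. A reader of Table 2.0010 would probably take it for one or the other. The population has had at least three prior lines (section 2.3), so death before a further line is a plausible first event.

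The second point is independent of the first. A subject need not respond to have a TTNT, yet whether there are enough data to summarise it is judged on responders only. Non-responders who move to new therapy would not count towards that decision.

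**Working it through.** **No planned figure to reproduce.** The SAP gives no expected TTNT median, event count or untreated-death rate. The following is an illustration on assumed inputs.

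**Inputs**
- Event and censoring rule: section 7.3.1.
- Estimator: not stated. Kaplan-Meier is inferred from the censoring rule, the median and quartiles, and the TTE1 shell.
- Assumed: constant hazards, h1 for next treatment and h2 for death without next treatment; h1 = ln 2 / 6 or ln 2 / 9 per month; h2 = 20% or 30% of h1.

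**Formulas**
- Kaplan-Meier median with death censored: ln 2 / h1. It does not contain h2.
- Cumulative-incidence median: the t that solves h1/(h1+h2) × (1 − exp(−(h1+h2)t)) = 0.5.
- Median of next treatment or death: ln 2 / (h1+h2).

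**Example, 6-month median, h2 = 20% of h1**
- h1 = 0.6931/6 = 0.1155; h1+h2 = 1.2 × 0.1155 = 0.1386.
- Kaplan-Meier: 6.0 months.
- Cumulative incidence: 1 − exp(−0.1386t) = 0.5 × 1.2 = 0.60, so t = −ln(0.40)/0.1386 = 0.9163/0.1386 = 6.6 months.
- Composite: 6/1.2 = 5.0 months.

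At 30%: t = −ln(0.35)/0.1502 = 1.0498/0.1502 = 7.0 months, and the composite is 6/1.3 = 4.6 months.

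| h1 median | h2/h1 | Kaplan-Meier median | Cumulative-incidence median | Composite median |
|---|---|---|---|---|
| 6 months | 20% | 6.0 | 6.6 | 5.0 |
| 6 months | 30% | 6.0 | 7.0 | 4.6 |
| 9 months | 20% | 9.0 | 9.9 | 7.5 |
| 9 months | 30% | 9.0 | 10.5 | 6.9 |

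(For 9 months the cumulative-incidence values are 0.9163/0.0924 and 1.0498/0.1001; the composites are 9/1.2 and 9/1.3.)

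**Heavier mortality.** Now let untreated deaths be a given share of first events, with a 9-month median. At 20%, 30% and 40% the Kaplan-Meier median is 9.0 months each time. The cumulative-incidence median is 10.2, 11.4 and 14.0 months, and the composite median 7.2, 6.3 and 5.4 months. At 50% the cumulative-incidence median is never reached, while Kaplan-Meier still returns 9.0.

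**Responder condition.** Section 7.2.2.2 uses similar wording for duration of response: "If there are sufficient number of responders who subsequently progress or die due to PD, distribution of DOR will be summarized using the Kaplan-Meier method". There it fits, because that endpoint exists only among responders. TTNT is defined without reference to response, and section 7.3.3 and Table 2.0010 both say All Treated. The condition in 7.3.2 therefore does not match the endpoint it governs.

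**The case against.** The strongest reply is that the rule is explicit and reproducible: origin, event and censoring date are all stated. A cause-specific TTNT is a legitimate target. Failure including death is already covered, since progression-free survival counts death from any cause and overall survival is analysed. TTNT is listed under other efficacy analyses, is not among the objectives in section 2.2, and no hypothesis rests on it. Kaplan-Meier is not named for it, and every rate above is assumed.

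Most of this stands and limits the weight of the point. It does not remove it. The SAP nowhere says that a cause-specific target is intended, and a median taken from such a curve would still not describe what happened to the treated subjects.

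A reader might go further in two ways that the documents do not support:

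- **That the reported median grows longer as more subjects die untreated, or that correcting it must shorten it.** Under constant hazards the censored median is ln 2 / h1 whatever the death rate. It is longer than the composite median but shorter than the cumulative-incidence median, so the direction depends on the target chosen.
- **That the responder wording biases the median or limits the analysis to responders.** As written it only decides whether the summary is produced. Table 2.0010 lists All Treated without that condition.

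**Conclusion.** The point holds as a limited one. Section 7.3.1 censors a competing event, and section 7.3.2 reports quantiles without saying how they are estimated. If Kaplan-Meier is used, the median belongs to a setting without untreated death. In the illustration with a 6-month median, it differs from the cumulative-incidence median by 0.6 or 1.0 month and from the composite median by 1.0 or 1.4 months, in opposite directions. These sizes rest on constant hazards, on death rates that the SAP does not give, and on an inferred estimator.

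The responder condition is a separate inconsistency of wording with no effect on the median. Both matters concern a descriptive endpoint and leave the primary overall response rate conclusion untouched.

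**What to change.** - **Section 7.3.1:** keep next treatment as the event, and state that death without next treatment is a competing event.
- **Section 7.3.2:** name the estimator, and report the cumulative incidence of next treatment with its median and quartiles where reached. Time to next treatment or death may be added as a clearly labelled supportive composite.
- **Section 7.3.2, separately:** replace *responders* with *subjects* in the condition, so that it agrees with section 7.3.3 and Table 2.0010.

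The cost is a few words of text, an event code that separates death from other censoring, and a little more analysis for Table 2.0010. No new data are needed. Under the assumptions above, the cumulative-incidence median will be longer than the Kaplan-Meier one and the composite median shorter, so each must be labelled for what it estimates.
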